8.3.3 Classification of an Adverse Event

The SAFE EVICT CORONA-ALI trial will utilize the Common Terminology Criteria for Adverse Events (CTCAE) v5.0, published: November 27, 2017, which grades 1 through 5 with unique descriptions of severity for each adverse event based on the following:

Severity of Event

Grade 1 Mild; asymptomatic or mild symptoms; clinical or diagnostic observations only; intervention not indicated

Grade 2 Moderate; minimal, local or noninvasive intervention indicated; limiting age appropriate instrumental activities of daily living (ADL).

Grade 3 Severe or medically significant but not immediately life-threatening; hospitalization or prolongation of hospitalization indicated; disabling; limiting self-care or ADLs.

Grade 4 Life-threatening consequences; urgent intervention indicated.

Grade 5 Death related to AE.

Relationship to Study Intervention

All adverse events AEs will have their relationship to study intervention assessed by the investigator who examines and evaluates the participant based on temporal relationship and his/her clinical judgment. The degree of certainty about causality will be graded using the categories below. In a clinical trial, the study product must always be suspect.

- Related — The AE is known to occur with the study intervention, there is a reasonable possibility that the study intervention caused the AE, or there is a temporal relationship between the study intervention and event. Reasonable possibility means that there is evidence to suggest a causal relationship between the study intervention and the AE.
- Not Related — There is not a reasonable possibility that the administration of the study intervention caused the event, there is no temporal relationship between the study intervention and event onset, or an alternate etiology has been established.

Expectedness

The Principal and Sub-Investigators will be responsible for determining whether an adverse event (AE) is expected or unexpected. An AE will be considered unexpected if the nature, severity, or frequency of the event is not consistent with the risk information previously described for the study intervention.

8.3.4 Time Period and Frequency for Event Assessment and Follow-Up

The occurrence of an adverse event (AE) or serious adverse event (SAE) may come to the attention of study personnel during study visits and interviews of a study participant presenting for medical care, or upon review by a study monitor.

All AEs including local and systemic reactions not meeting the criteria for SAEs will be captured on the appropriate electronic case report form (eCRF). Information to be collected includes event description, time of onset, clinician's assessment of severity, relationship to study product (assessed only by those with the training and authority to make a determination), and time of resolution/stabilization of the event. All AEs occurring while on the study must be documented appropriately regardless of relationship. All AEs will be followed to an adequate resolution.

Any medical condition that is present at the time that the participant is screened will be considered as a baseline and not reported as an AE.

Changes in the severity of an AE will be documented to allow an assessment of the duration of the event at each level of severity to be performed. AEs characterized as intermittently require documentation of onset and duration of each episode.

The study personnel will record all reportable events with start dates occurring any time after informed consent is obtained until 7 (for non-serious AEs) or 30 days (for SAEs) after the last day of study participation. At each study visit, the investigator will inquire about the occurrence of AE/SAEs since the last visit. Events will be followed for outcome information until resolution or stabilization.

8.3.5 Adverse Event Reporting

Investigators will report all unanticipated problems that involved risk or harm to a research participant AND was not anticipated or foreseen (e.g., not described in the consent form) AND is probably or definitely related to or caused by the research to the IRB within 5 business days of receiving notice of the unanticipated problem.

Investigators will report all unanticipated problems, defined as a problem that involve risk or harm to a research participant AND was not anticipated or foreseen (e.g., not described in the consent form) AND is probably or definitely related to or caused by the research, to the DSMB within 7 calendar days of the being notified of the event.

Investigators will also determine if the serious adverse event is unexpected for Vitamin C. Unexpected for Vitamin C is defined as any event not listed in the Vitamin C package insert. If the investigator determines that any serious and study-related adverse event is unexpected

for Vitamin C, the FDA will be notified within 7 calendar days. Such events may also meet the definition of Unanticipated Problems as described below.

CTCAE Grade 3 or higher will trigger a pause in enrollment while the DSMB reviews the data to determine whether subsequent enrollment should proceed.

Examples of untoward clinical occurrences or disease-related events (DRE) that are expected in the course of COVID-19 include: 1) transient or worsening hypoxemia, 2) agitation, 3) delirium, 4) nosocomial infections, 5) skin breakdown, 6) acute hepatitis, 7) **acute kidney injury**, and 8) worsening of respiratory function. Such events, which are often the focus of prevention efforts as part of usual ICU care, will not be considered reportable adverse events unless the event is considered by the investigator to be associated with the study drug or procedures, or unexpectedly severe or frequent for individual patient sepsis and AH.

Examples of unexpectedly frequent untoward clinical occurrences would be repeated episodes of unexplained hypoxemia. This would be in contrast to an isolated episode of transient hypoxemia (e.g., SpO₂ ~85%), related to positioning or suctioning. This latter event would not be considered unexpected by nature, severity or frequency. These events will be captured in the eCRF.

8.3.6 Adverse Events, Serious Adverse Events, and Unanticipated Problems

Adverse events (AEs), serious adverse events (SAEs), and unanticipated problems (UPs) occurring at VCU will be managed and reported in accordance with [VCU/VCUHS Clinical Research Standard Operating Procedures #CR-RE-300.1: Adverse Event Management and Reporting](#). Those occurring at the VA will be managed and reported in accordance with the VA's standard operating procedures.

All serious adverse events (SAEs) will be followed until a satisfactory resolution or until the site investigator deems the event to be chronic or the participant is stable.

The PI/sponsor will be responsible for notifying the Food and Drug Administration (FDA) of any unexpected fatal or life-threatening suspected adverse reaction as soon as possible, but in no case later than 7 calendar days after being informed about the event. In addition, the PI/sponsor must notify FDA and all participating investigators in an Investigational New Drug (IND) safety report of potentially serious risks, from clinical trials or any other source, as soon as possible, but in no case later than 15 calendar days after the PI/sponsor determines that the information qualifies for reporting.

[figure not shown]
9 - Statistical Considerations

[figure not shown]
[figure not shown]
Model Set-Up:

We plan to use a two-sample, unequal-variance 2-tail t-test for comparing the mean differences between the two groups, the vitamin C arm and placebo arm. The actual interventions will be blinded and will be revealed after the completion of statistical analysis, therefore, we will be labeled as group A and group B. No one besides the DSMB and independent statistician supporting the DSMB will have access to the comparative data, even if the treatment groups are masked as group A and Group B.

[figure not shown]
This is a proof-of-concept study, **with predetermined sample sizes** for each arm, which is 30 patients for group A and 30 patients for group B, therefore the **power analysis is driven by the predetermined sample size and did not determine the sample size.**

[figure not shown]
Therefore, this proof-of-concept study of 60 patients, 30 allocated to the treatment arm and 30 to the placebo arm, will have 96% power (1-beta (β)) to detect an **average of 1-point difference** in the primary outcome, the WHO COVID-19 ordinal scale, with an alpha error probability (α) of 4% (0.04). This is by applying a two-tail, t-test with unequal variances (see figure below).

[figure not shown]

For binary secondary outcomes, we plan to use the chi-squared test, with 1-degree of freedom. The expected effect size for an alpha level of 0.05 and power of 80% is 0.36, as shown in the figure below.

In contrast, for a constant hypothetical effect size of 0.2, a phase 3 trial will require at least 200 patients to achieve a power of 80% and an alpha of 0.05 (yellow line, figure below).

Planned Interim Analyses:

No planned interim analyses will be conducted in this study. The results will be analyzed after the 60th patient has finished enrollment and has been discharged from the hospital (phase 1). There are no provisions to stop the trial early for efficacy.

Missing Data

The primary outcome, the WHO-COVID-19 scale is encompassing missing data from death or hospital discharge. Missing laboratory or clinical data due to patient death, or discharge will not be imputed given this practice will introduce systematic bias, since they are not missing at-random. For organ-system data, the highest scores will be attributed after patient death, since death causes cessation of all organ function, and any imputation method will underestimate the severity. For missing-at-random data, multiple imputation with a pattern-mixture model with control-based pattern imputation will be used, with 50 imputed data sets, in order to compensate for data that may be missing at random.

10 - Supporting Documentation and Operational Considerations

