CLINICAL STUDY PROTOCOL

C. Kenneth and Dianne Wright
Center for Clinical and Translational Research

SAFEty Study of Early Infusion of Vitamin C for Treatment of Novel Coronavirus Acute Lung Injury

(SAFE EVICT CORONA-ALI)

Protocol Version: 1.83

Protocol Version IRB approved: 08/10/2021

VCU IRB Number: HM20018977

ClinicalTrials.gov Identifier: NCT04344184

IND: 149518

Study Personnel

Principal Investigator(s) [name]
Virginia Commonwealth University
Department of Internal Medicine
Pulmonary and Critical Care Medicine

[name], MD
Virginia Commonwealth University
Department of Internal Medicine
Pulmonary and Critical Care Medicine

Co-Investigators
[name]
Central Virginia VA Health System
Department of Internal Medicine
Gastroenterology and Hepatology Division

[name]
Department of Biostatistics
Virginia Commonwealth University,
Massey Cancer Institute

[name]
Virginia Commonwealth University
Department of Surgery
Division of Trauma Surgery

[name]
Virginia Commonwealth University
Department of Surgery
Division of Trauma Surgery

Clinical Coordinators: [name] and [name]
Virginia Commonwealth University
Department of Internal Medicine
Pulmonary and Critical Care Medicine

Regulatory Contact: [name]
Virginia Commonwealth University
Department of Internal Medicine
Pulmonary and Critical Care Medicine

Synopsis

Study Description

The purpose of this proof-of-concept, phase 2 safety study is to examine the safety profile, and possible therapeutic effects of high-dose, intravenous vitamin C (HDIVC) compared to placebo in hospitalized adult patients with novel Coronavirus COVID-19 and hypoxemia.

Objectives

To assess the safety profile of a 4-day (96-hour) intravenous vitamin C treatment protocol (comprised of four intravenous infusions a day, that is 50 mg/kg every 6 hours) in patients with laboratory-confirmed SARS-CoV-2 infection manifesting COVID-19 (Novel Coronavirus Disease 2019) with hypoxemia. While performing this phase 2 proof-of-concept, safety study, we will explore the following hypotheses:

Endpoint

Primary Endpoint (Safety): HDIVC infusion does not worsen the patients' outcomes, as measured by differences in the mean 9-point (from 0 to 8) World Health Organization (WHO) ordinal scale for disease improvement, between the two populations at 28, 60 and 90 days:

Table 1.

Patient State	Descriptor	Score
Uninfected	No clinical or virologic evidence of infection	0
Ambulatory	No limitation of activities	1

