5.1 Inclusion Criteria

- Adults of 18 years or older
- Patients hospitalized with a diagnosis of COVID-19 based on central laboratory-confirmed COVID-19 Novel Coronavirus Disease-2019, based on a positive SARS-CoV-2 RT-PCR confirmed **within 72 hours** prior to enrollment of nasal, oropharyngeal, or BAL specimen with hypoxemia, (i.e., decrease in oxygenation, as outlined below)
- Pulse oximetry saturation (SpO₂) < 93% on room air in WHO COVID-19 ordinal scale 3 patients, regardless the need for assisted ventilation, or oxygenation.
- Any new requirement of supplemental oxygen, with any oxygen device (WHO COVID-19 ordinal scale 4-7, regardless of pulse oximetry reading)
- In patients with supplemental oxygen at home, **any increase** in the requirement of supplemental oxygen.
- In ICU level of care

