5.5 Strategies for Recruitment and Retention

Non-intubated patients with COVID19 will be recruited from the Emergency Department (ED), the medicine inpatient wards, and the intensive care units (ICU) at VCU Medical Center and the Central Virginia VA Health System in Richmond, Virginia (RICVA). Both institutions are tertiary care medical centers with a large referral base. Study personnel will review patients within the electronic medical record to identify potential candidates for enrollment. Permission to approach patients and/or their families will be requested from the attending physicians in charge of patient care in the ED, inpatient unit, or the ICU. All patients meeting the inclusion/exclusion criteria will be approached with consent and will be entered into a screening log. If the patient is not enrolled, the screening log will include information explaining why enrollment did not occur (exclusion criteria, attending physician denial, patient refusal, etc.).

6 - Study Intervention

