6.3 Measures to Minimize Bias: Randomization and Blinding

The investigational pharmacist will use a standardized scientific randomization module within REDCap (36) Only the study pharmacist will have access to the online secure repository. The REDCap module has an auditing trail and log records on who accesses it as well as strict security controls.

The prepared infusion bags will have **sealed** amber shrouding to cover the IV bag in order to maintain the blind.

The randomization method will be a block (per site) and stratified and WHO COVID-19 ordinal outcomes status) randomization.

We plan to perform block randomization for each participating site. Within this block, there will be further stratification of randomization for severity of illness based on WHO COVID-19 ordinal outcome cutoff as seen in the table below:

	WHO COVID-19 scale 3-5 at enrollment	WHO COVID-19 scale 6-7 at enrollment
	Stratum A	Stratum B

The goal is for each site to have an equivalent severity among patients randomized to the treatment or placebo arm within each stratum.

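### Randomization is stratified by site and WHO severity, but the planned tests ignore both; if severity predicts outcome, the tests are conservative and less able to see harm than an adjusted analysis.

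*Combined protocol and SAP*

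**What the plan says.** **Design.** Section 6.3 states "We plan to perform block randomization for each participating site" and, within site, "there will be further stratification of randomization for severity of illness based on WHO COVID-19 ordinal outcome cutoff". The cut is WHO 3-5 against WHO 6-7 at enrollment. The stated aim is equal severity between arms within each stratum. No block size is given.

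**Analysis.** Section 9 (Model Set-Up) gives the primary test: "We plan to use a two-sample, unequal-variance 2-tail t-test for comparing the mean differences between the two groups". For the rest: "For binary secondary outcomes, we plan to use the chi-squared test, with 1-degree of freedom". The power statement is for the same plain two-tail t-test: "30 allocated to the treatment arm and 30 to the placebo arm, will have 96% power" for a 1-point difference at alpha 0.04. No readable text uses site, stratum or baseline WHO score as a covariate or stratifier in any test. The only mention of adjustment is a consideration recorded in the amendment history, which is not a current analysis rule. Some Section 9 figures are not shown.

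**Who fills the upper stratum.** Section 5.1 admits "Any new requirement of supplemental oxygen, with any oxygen device (WHO COVID-19 ordinal scale 4-7, regardless of pulse oximetry reading" and requires ICU level of care. Section 5.5 says "Non-intubated patients with COVID19 will be recruited from the Emergency Department (ED" and other units. WHO 6 and 7 are ventilated states, so these sections disagree on whether the WHO 6-7 stratum has any patients.

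**The concern.** The stratifier is a two-level cut of the scale that serves as the primary outcome, so it plausibly predicts that outcome. Balancing arms on a prognostic factor makes the arm difference less variable. A t-test that ignores the factor estimates its standard error from the full variance, between-stratum part included, so the standard error is too large. The test then rejects less often than its nominal level and has less power than one that uses the strata. The same holds for the chi-squared test.

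The direction matters because the Synopsis words the primary endpoint as a claim of no harm: "Primary Endpoint (Safety): HDIVC infusion does not worsen the" outcomes of the patients. A non-significant two-sided test is easily read as reassurance, and a conservative test makes that result more likely when harm is real. With the sample size fixed at 60, the analysis is one of the few places where information can be recovered.

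**Working it through.** **1. Inputs from the plan.** 30 per arm; 1-point difference; two-sided alpha 0.04; stated power 96%. For binary outcomes: effect size w = 0.36, alpha 0.05, power 80%. No SD is readable.

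**2. Reproducing the stated figures.** With SD = 1, SE = 1 × √(2/30) = 0.258 and 1/0.258 = 3.873. The normal approximation gives Φ(3.873 − 2.054) = 96.6%; the noncentral t with 58 df gives 96.0%. So the stated power implies an SD of about 1. For chi-squared, 60 × 0.36² = 7.78, which gives 79.6% power. Both statements reproduce, and neither uses the strata.

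**3. Closed form.** Let balanced strata explain a share R² of outcome variance, and let SE be the unadjusted standard error.

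- SE inflation: 1/√(1 − R²)
- Actual type I error of the unadjusted test: 2[1 − Φ(2.054/√(1 − R²))]
- Unadjusted power: Φ((δ/SE − 2.054)/√(1 − R²))
- Adjusted power: Φ(δ/(SE√(1 − R²)) − 2.054)

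At R² = 0.1 the inflation is 1/0.949 = 1.054 and type I error is 2[1 − Φ(2.165)] = 0.030. At R² = 0.3 type I error is 2[1 − Φ(2.455)] = 0.014. Power for a 1-point difference, unadjusted to adjusted:

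| SD | R² = 0.1 | R² = 0.3 |
|---|---|---|
| 1 | 97.2 to 97.9% | 98.5 to 99.5% |
| 2 | 45.1 to 49.5% | 44.4 to 60.3% |
| 2.5 | 29.7 to 33.7% | 27.3 to 42.0% |

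A simulation with normal outcomes, permuted blocks of 4, 40% in the upper stratum and 70% at one site agrees: the t-test has type I error 0.032 at R² = 0.1 and 0.018 at R² = 0.3, and the adjusted model stays at 0.041.

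**4. Simulation on the WHO scale.** All of the following are assumptions: 60 patients, sites split 80/20, blocks of 4, a proportional-odds harm (log OR 0.8, equal to 1.0-1.2 points), total SD 2.6-2.9, and three pairs of day-28 mortality by stratum. Survivors on WHO 1-7 were distributed 30/35/8/10/6/7/4% in the lower stratum and 12/30/10/15/8/17/8% in the upper. The adjusted model has treatment, severity and site, with HC2 standard errors and 56 df. There were 10,000 trials per scenario.

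| Split 3-5 / 6-7 | Mortality by stratum | R² | Mean SE / true SD | Power, t-test to adjusted |
|---|---|---|---|---|
| 54/6 | 25/45% | 3% | 1.002 | 35.0 to 35.6% |
| 54/6 | 20/50% | 5% | 1.022 | 34.8 to 36.1% |
| 54/6 | 15/60% | 10% | 1.031 | 31.5 to 34.5% |
| 48/12 | 25/45% | 5% | 1.015 | 33.3 to 34.9% |
| 48/12 | 20/50% | 9% | 1.060 | 32.5 to 35.1% |
| 48/12 | 15/60% | 17% | 1.077 | 28.8 to 33.9% |
| 30/30 | 25/45% | 8% | 1.045 | 31.3 to 34.1% |
| 30/30 | 20/50% | 14% | 1.071 | 27.7 to 32.5% |
| 30/30 | 15/60% | 24% | 1.138 | 20.7 to 29.6% |

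The t-test's type I error at nominal 0.04 was 0.041-0.034 (54/6), 0.038-0.029 (48/12) and 0.032-0.020 (30/30). The adjusted model held 0.039-0.042 throughout.

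**5. Day-28 mortality, chi-squared against a severity-stratified Cochran-Mantel-Haenszel test, alpha 0.05.** From mild to strong prognosis, power goes from 30.3 to 30.9% up to 20.6 to 23.1% (54/6), from 29.5 to 30.5% up to 19.8 to 25.0% (48/12), and from 31.1 to 32.2% up to 18.6 to 25.3% (30/30). Type I error is 0.027-0.049 for chi-squared and 0.048-0.052 for the stratified test.

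**6. Boundary cases (5,000 trials each).**

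- Strata not prognostic: 36.4 to 36.1% (30/30) and 35.6 to 35.4% (54/6), so adjustment costs 0.2-0.3 points.
- SD 1, 30/30, stratum explaining 3, 10 or 24%: 96.2 to 96.4%, 96.6 to 97.5%, 97.5 to 99.0%.
- Site alone, differing by 0.25 or 0.5 SD: 28.7 to 29.0%, 27.5 to 29.0%.

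**The case against.** The strongest reply is that nothing is lost against the plan's own claim. At the SD of 1 implied by the stated 96%, the unadjusted test keeps 96.2-97.5% power and adjustment adds at most 1.5 points. This stands: the loss is relative to an adjusted analysis, not to the 96%.

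The larger gains rest on an SD, stratum split, prognostic strength, site split and block size that the readable text does not give, and the SD may be in a figure not shown. That also stands, which is why only a range is offered. At 54/6 with mild prognosis the type I error is nominal and the gain is 0.6 points. The simulated outcomes are built on day-28 mortality, so prognostic strength at days 60 and 90 was not examined.

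The direction of the error depends on how the no-harm claim is judged. If it were read from a confidence interval, an over-wide standard error would make the claim harder to support. The plan states no such rule; it names a two-tail test, for which conservatism means harm is missed more often. The DSMB also reviews serious adverse events narratively, so harm detection does not rest on this test alone. That lowers the stakes but leaves the comparative analysis unchanged.

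Finally, a test stratified by severity only still ignores site. This is deliberate: site adds 0.3-1.5 points on the primary outcome, and four cells are sparse at 60 patients (43/11/5/1 under the 54/6 split).

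**Conclusion.** The concern holds. In the readable text the analysis does not use the factors on which randomization is stratified. The estimate is unbiased and type I error is not inflated; the cost is efficiency. Under the assumed SD of 2.6-2.9, the standard error is 0-14% too wide, type I error ranges from about 0.041 to 0.020, and adjustment gains 0.6-3.0, 1.6-5.2 or 2.9-8.9 power points at splits 54/6, 48/12 and 30/30 (differences taken before rounding). The gain for day-28 mortality is 0.6-6.7 points. The effect therefore runs from near zero to moderate, and depends mainly on how many WHO 6-7 patients enrol and how strongly severity predicts outcome. If Section 5.5 governs and that stratum is empty, the severity part disappears. The low absolute power of 21-35% for the t-test comes from the assumed SD, not from the missing covariate. The change is worth making because it costs almost nothing if the strata are uninformative.

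**What to change.** - **Primary analysis.** Prespecify a linear model for the WHO score with treatment, severity stratum and site as main effects, optionally with baseline WHO score, and small-sample robust (HC2) standard errors.
- **Binary outcomes.** Use a Cochran-Mantel-Haenszel test stratified by severity only.
- **Sparse cells.** Fit no site-by-severity interaction. If cells are too thin, drop site first. Merge the severity strata only if one stratum has no patients in an arm.
- **Sensitivity.** Keep the unadjusted t-test and chi-squared test.
- **Consistency.** Reconcile Section 5.5 with Sections 5.1 and 6.3 on intubated patients, and state the expected share at WHO 6-7.

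The cost is analysis-plan wording and two or three of 58 degrees of freedom. Site and baseline WHO score are already needed to randomize, so no new data are required. The change should be fixed before unblinding, since adjustment chosen afterwards would look data-driven.

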	Limitation of Activities	2
Hospitalized mild disease	Hospitalized, no oxygen therapy	3
	Oxygen by mask or nasal prongs	4
Hospitalized Severe Disease	Non-invasive ventilation or high-flow oxygen	5
	Intubation and mechanical ventilation	6
	Ventilation + additional organ support – vasopressors, renal replacement therapy, ECMO	7
Dead	Death	8

Secondary Endpoint A (Safety): Daily renal safety biomarkers on the day of randomization (Day 0), then day 1-7. These include (1) daily serum oxalate levels, (2) daily urine microscopic analysis for the presence of oxalate stones (3) daily random urine oxalate and 24-hour urine oxalate levels on days 5,7 and 14.

Secondary Endpoint B (Safety): acute kidney injury-free days at day 28, 90 (stemming from daily AKI assessment while patient is in the hospital).

Secondary Endpoint C (Safety): All-cause mortality to day 28, 60 90 (daily assessment).

Secondary Endpoint D: (Exploratory): COVID-19 and sepsis-specific inflammatory marker levels on Day 0, then on day 7. These include (1) ferritin, (2) D-dimer, (3) lactate dehydrogenase (LDH), (4) interleukin-6, and (5) Trough ascorbate plasma concentrations at 24 hours, 48 hours, 96 hours and final plasma concentration assessment at 168 hours.

Secondary Endpoint E: (Safety): Proportion of patients alive and free of respiratory failure through 28-days. (Respiratory failure defined as resource utilization requiring at least 1 of the following: Endotracheal intubation and mechanical ventilation, Oxygen delivered by high-flow nasal cannula (heated, humidified, oxygen delivered via reinforced nasal cannula

at flow rates >20L/min with fraction of delivered oxygen ≥ 0.5), noninvasive positive pressure ventilation, extracorporeal membrane oxygenation).

Secondary Endpoint F: (Safety): Proportion of patients alive and free of invasive mechanical ventilation at 28-days.

CLINICAL STUDY PROTOCOL

C. Kenneth and Dianne Wright
Center for Clinical and Translational Research

Study Population

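### Section 9's only test for means is an unadjusted Welch t-test; applied by default to serum oxalate and the inflammatory markers, it would leave the day-0 values, the log scale and the repeated oxalate samples unused

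*Combined protocol and SAP*

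**What the plan says.** Section 9, Model Set-Up, states: "We plan to use a two-sample, unequal-variance 2-tail t-test for comparing the mean differences between the two groups". The sentence names no endpoint, day, scale or covariate. The power statement that follows applies the test to a difference "in the primary outcome, the WHO COVID-19 ordinal scale". Binary secondary outcomes get a chi-squared test. The readable text assigns no method to a continuous laboratory secondary.

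The data available for those endpoints are:

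- **Serum oxalate** (Synopsis, Secondary Endpoint A): "Daily renal safety biomarkers on the day of randomization (Day 0), then day 1-7".
- **Inflammatory markers**: day 0 and day 7 in Synopsis Secondary Endpoint D; day 7 in the section 3.1 table. Section 8.1.1 instead schedules biomarker draws at hours 0, 48, 96 and 168.
- **Completeness**: the footnotes to the Schedule of Activities make research labs on days 1-4 add-ons to clinical draws, with no dedicated stick.

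On missing values, section 9 says: "Missing laboratory or clinical data due to patient death, or discharge will not be imputed given this practice will introduce systematic bias". It adds that such data are not missing at random. For data that are missing at random it plans control-based multiple imputation with 50 data sets.

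**The concern.** Section 4.2 makes possible kidney harm a central question, and the section 3.1 table relies on serum oxalate, urinalysis and urine oxalate to show how oxalate nephropathy might arise. With 30 patients per arm, the method used to read those measurements matters. A two-sample t-test on one day's concentrations uses neither the patient's own starting value nor the other days' samples. If concentrations are right-skewed, as I assume, it also works on an inefficient scale. In a safety trial, an insensitive test can give false reassurance. With no contrast named, up to seven daily oxalate comparisons are possible, and nothing says which one counts.

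**Working it through.** **1. The plan's own figure.** The plan says the trial "will have 96% power" for an "average of 1-point difference" on the WHO scale at two-sided alpha 0.04. Noncentral-t power with 30 per arm and SD 1.0 is 96.0%, so the figure reproduces. The SD is not in the readable text; 1.00 is the value that gives 96%. Power would be 92% at SD 1.1, 68% at 1.5 and 44% at 2.0. No power is stated for any laboratory endpoint.

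**2. Inputs for the laboratory comparison.** From the plan: 30 per arm. Two-sided alpha is taken as 0.05. Assumed, because the documents give none: lognormal values, true ratio 1.6, log SD 0.8, baseline to follow-up correlation r = 0.2 to 0.6, between-day correlation ρ = 0.65, the same ratio on every day, and complete samples.

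**3. Raw single-day Welch test.** There is no simple closed form for skewed data. Simulation gives about 48-50%.

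**4. Log scale, single day, no baseline.** Standardized difference d = ln(1.6)/0.8 = 0.470/0.8 = 0.5875. Noncentrality = d × √(30/2) = 0.5875 × 3.873 = 2.28. Power is 61%.

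**5. Add the log day-0 value, and then four days.** For one day, adjustment multiplies the variance by 1 − r². For the mean of four days the factor is (1 + 3ρ)/4 − r². Dividing d by the square root of the factor gives:

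| Analysis | r | Factor | Effective d | Power, formula | Power, simulated |
|---|---|---|---|---|---|
| One day | 0.2 | 0.960 | 0.600 | 63% | 62% |
| One day | 0.4 | 0.840 | 0.641 | 68.5% | 66-68% |
| One day | 0.6 | 0.640 | 0.734 | 80% | 77-79% |
| Four-day mean, ρ = 0.65 | 0.2 | 0.7375 − 0.04 = 0.6975 | 0.703 | 76% | 75-76% |
| Four-day mean, ρ = 0.65 | 0.4 | 0.7375 − 0.16 = 0.5775 | 0.773 | 84% | 83-84% |
| Four-day mean, ρ = 0.65 | 0.6 | 0.7375 − 0.36 = 0.3775 | 0.956 | 95% | 95-96% |
| Four-day mean, ρ = 0.85 | 0.2 | 0.8875 − 0.04 = 0.8475 | 0.638 | 68% | 67% |

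**6. Where the gain comes from.** At r = 0.2 the log scale lifts single-day power from about 48-50% to 61%; the day-0 value adds only 1 to 2 points more. At r = 0.6 the day-0 value adds 16 to 18 points (61% to 77-79%). Averaging days helps most when days are less correlated with each other.

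**7. Other spreads (r = 0.4-0.6, ρ = 0.65).** In the order raw, adjusted single day, adjusted four-day mean, log SD 1.0 gives about 28-31%, 48-60% and 64-84%. Log SD 0.6 gives about 77-78%, 90-95% and 98-100%.

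**8. Validity.** With no true difference and log SD 1.0, the raw test rejected in about 3-4% of simulated trials. The issue is sensitivity, not false positives.

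**The case against.** The strongest objection is that the plan makes no such commitment. A reader might infer that section 9 prescribes seven unadjusted daily t-tests on raw values. It does not: the sentence names no marker, day or scale, and several section 9 figures are not shown. That stands, and it is why the point concerns a default. If the test was never meant for these endpoints, they have no stated method in the readable text, and the repair is the same. Reading the sentence as change from day 0 does not help: a t-test on raw change has about 31%, 36%, 44% and 58% power at r = 0, 0.2, 0.4 and 0.6, below the log-scale adjusted analysis throughout.

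Four other limits stand.

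- A reader might infer that the plan discards samples from patients who later die or leave. It declines to impute missing values; it drops no observed one.
- The endpoint definition gives the inflammatory markers a single follow-up day, so the four-day gain belongs to oxalate. Those markers are exploratory, and the nephropathy role belongs to the oxalate and urine measures.
- The size rests on assumed inputs. At a ratio of 2.5, or at log SD 0.4, the raw test already has about 95% power or more. Add-on sampling on days 1-4 would reduce the four-day gain.
- A mixed model assumes missing at random, which section 9 denies for death and discharge. It uses observed samples better but does not remove that difficulty.

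**Conclusion.** The point holds as a default left open: the only stated method for means ignores information that the trial already plans to collect. Under the assumptions above, a log-scale baseline-adjusted analysis gains roughly 12 to 30 points on a single day. Using four on-treatment days gains roughly 25 to 47 points for oxalate, or somewhat under 20 if days are highly correlated and the baseline is weakly informative. The direction is secure for skewed markers with moderate effects; the size is not, because no variance, correlation or expected ratio is given.

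A reader might also infer that the trial's overall power is compromised. It is not: the stated 96% concerns the WHO scale, and the plan says its "power analysis is driven by the predetermined sample size and did not determine the sample size". The matter is confined to the continuous laboratory secondaries, where a change is worthwhile because it is nearly free.

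**What to change.** Add to section 9:

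1. **Serum oxalate.** Analyze log values in a repeated-measures model with log day-0 value, arm, day, arm-by-day, site and WHO stratum (scale 3-5 or 6-7, as in section 6.3). Name one contrast, the average arm ratio over days 1-4, reported as a geometric mean ratio with confidence interval. Show daily ratios descriptively.
2. **Ferritin, D-dimer, LDH, CRP and IL-6.** Analyze log day-7 values by ANCOVA on log day-0 value, site and WHO stratum. First reconcile the endpoint definitions in the Synopsis and section 3.1 with the draws in section 8.1.1.
3. **Missing samples.** State that all observed samples are used and nothing is imputed after death or discharge. Acknowledge that the mixed model assumes missing at random whereas section 9 says these data are not, and prespecify a sensitivity analysis for that departure.

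The cost is a few lines of text, slightly more programming and an explicit modelling assumption about missing samples. No samples or patients are added, and the primary analysis does not change.
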